5.2 Method of Treatment Assignment

This is a multicenter, open-label study to evaluate the safety, tolerability, PK, and preliminary efficacy of HMPL-523 in patients with relapsed or refractory lymphoma. Patients will be assigned to dose levels sequentially in the dose escalation stage. In the dose expansion stage, patients will be assigned by the sponsor. Upon completion of all screening evaluations and verification that the patient has met all eligibility criteria, the sites will contact the sponsor to confirm patient eligibility.

5.3 Study Treatment

5.3.1 Formulation, Packaging, and Handling

Three strengths of HMPL-523 tablets (100, 150, and 200 mg based on the free base) will be used for clinical studies. The drug products are tablets that are packaged in white high-density polyethylene bottles. The tablets are composed of widely used pharmaceutical excipients (United States Pharmacopeia grade or equivalent) and HMPL-523 **CCI** drug substance. The tablets should be stored below 25°C.

For further details, see the HMPL-523 IB.

5.3.2 Drug Labeling

The investigational drug will be labeled as required by local regulations.

5.3.3 Drug Accountability

All study drugs required for this study will be provided by HUTCHMED Limited or the authorized contract research organization (CRO). The recipient will acknowledge receipt of the drug by completing and keeping the appropriate documentation form indicating shipment content and condition. Damaged supplies will be replaced.

Accurate records of all study drugs received by, dispensed from, and returned to the study site will be recorded in the source documentation.

The study drug will be disposed of at the study site according to the study site's institutional standard operation procedure and local regulations with the appropriate documentation upon approval of sponsor.

5.3.4 Dosage, Administration, and Compliance

Dose levels to be potentially tested in this study include 100, 200, 400, 600, and 800 mg/day orally.

The proposed dose of HMPL-523 is as specified in HMPL-523 should be taken with approximately 8 ounces (240 mL) of water under fed conditions, ideally within 30 minutes after meal but not later than 90 minutes after a meal (Table 1). Patients are advised to take QD dosage as required in cohorts/groups. All efforts should be made to ensure that the patient takes HMPL-523 at approximately the same time every day during their participation in the study and ideally within a ± 4 -hour window.

HMPL-523 should be taken with approximately 8 ounces (240 mL) of water under fed conditions, ideally within 30 minutes after meal but not later than 90 minutes after a meal (Table 1). The administration time should be accurately recorded in the patient diary.

In the study, patients will not be allowed to make up missed doses during any calendar day; patients will resume dosing at their next scheduled dose.

Guidelines for dosage modification and treatment interruption or discontinuation are provided in Sections 5.4 and 5.7.

Any overdose or incorrect administration of the study drug should be noted on the patient's source documentations and case report form (CRF). AEs associated with an overdose or incorrect administration of the study drug should be recorded on the patient's source documents and the AE page of the CRF.

5.3.5 Post-Trial Access to HMPL-523

The sponsor does not have any scheduled plans to provide HMPL-523 or any other study interventions for patients after the end of the study or for any patient who discontinues or withdraws from the study.

The sponsor will evaluate whether to continue providing HMPL-523 after the study is complete. In the event that the sponsor deems post-trial access to HMPL-523 to be appropriate, the sponsor may offer post-trial access to the HMPL-523 free of charge to eligible patients as outlined below.

A patient will be eligible to receive the study drug after the end of the study if all of the following conditions are met:

- The patient has relapsed/refractory lymphoma that requires continued study drug treatment for his or her wellbeing.
- The patient and his or her doctor comply with and satisfy any legal or regulatory requirements that apply to them.

A patient will not be eligible to receive the study drug after the end of the study if any of the following conditions are met:

- The study drug is commercially marketed in the patient's country and is reasonably accessible to the patient (ie, it is covered by the patient's insurance or would not otherwise create a financial hardship for the patient).
- The sponsor has discontinued development of the study drug for lymphoma in the specific region or data suggest that the study drug is not effective for lymphoma.
- The sponsor has reasonable safety concerns regarding the study drug as treatment for lymphoma.
- Provision of the study drug is not permitted under the laws and regulations of the patient's country.

5.4 Dose Delays and Modification

5.4.1 During Dose-Limiting Toxicity Assessment Window

If a patient experiences a TEAE of Grade 3 or Grade 4 and/or unacceptable toxicity including a DLT not attributable to the disease or disease-related processes under investigation, dosing will be interrupted and supportive therapy will be administered as required in accordance with local practices/guidelines.

Patients who experience a DLT may resume dosing at the same or the previous lower dose level at the discretion of the investigator if the toxicity is resolved or improved to baseline level. If a patient experiences an unacceptable toxicity at the reduced dose level, he/she will be discontinued from treatment. No patient will have his/her dose reduced by more than 2 dose levels. Once dose is reduced, it cannot be re-escalated.

If a clinically significant TEAE or unacceptable toxicity that does not meet the definition of a DLT is observed, the patient may receive subsequent doses to complete the dosing schedule, provided that the TEAE is improved to CTCAE Grade ≤ 2 within 2 weeks.

Dose reduction in patients without DLT is not permitted in the DLT assessment window without the sponsor's approval.

5.4.2 After Dose-Limiting Toxicity Assessment Window in Stage 1 or in Stage 2

After the DLT assessment window in Stage 1 or in Stage 2, the dose of HMPL-523 may be interrupted and/or reduced to the next lower dose level (600 mg) if any of the following are observed:

- Grade 3 or 4 hematologic toxicity
- Grade 3 or 4 nonhematologic toxicity (except for alopecia and skin eruption, nausea, vomiting, diarrhea, or constipation if well-controlled by systemic or topical medication)

Treatment with HMPL-523 should be withheld until the toxicity resolves to CTCAE Grade ≤ 2 . Dosing may then be resumed at either the same dose level or the previous lower dose level if the toxicity is improved to CTCAE Grade ≤ 2 within 2 weeks at the investigator's discretion. Consult with the sponsor if a treatment hold longer than 2 weeks is required for recovery from toxicity. If treatment is resumed at the same dose and the patient experiences the same toxicity over Grade 2, the dose should be reduced (600 mg) after resolution of the event. If the dose is reduced in Stage 2, additional PK sampling will be required at steady state (please refer to [Appendix 3](#) and Section 5.9.1). If the patient continues to experience unacceptable toxicity, a second dose reduction (400 mg) is permitted. Every patient is allowed to reduce dosing levels of HMPL-523 only twice. If a patient continues to experience unacceptable toxicity after 2 dose reductions, or if HMPL-523 dosing is interrupted for > 14 consecutive days due to toxicity, treatment should be discontinued, unless otherwise agreed between the investigator and the sponsor.

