
Grade 3 or Grade 4
 
(Severe or life-threatening symptoms, new or worsening hypoxia)
	
 • Hospitalize for further management • Request pulmonary and/or infectious disease consult • Evaluate differential diagnosis and causality (as described above) • Prompt treatment with antibiotic, antifungal, or appropriate treatment as per standard guidelines • Prompt treatment with systemic steroids, if considered immunerelated events 
 ○ Administer 1 to 2 mg/kg/day IV methylprednisolone or equivalent • Consider bronchoscopy and lung biopsy if clinically indicated 	
Withhold study drug
	
 • Continue close follow-up and re-imaging • If considered infectious etiology or if the etiology is unclear: 
 ○ If resolved to baseline within 28 days, resume study drug at a reduced dose ○ If not resolved to baseline within 28 days, permanently discontinue study drug ○ If recurs on restarting treatment, permanently discontinue study drug • If considered immune-related: 
 ○ Permanently discontinue study drug and treat promptly with steroids (including gradual tapering) 
 – If not improving after 48 hours or worsening, consider additional immunosuppression – After sustained clinical improvement is observed, gradually taper steroids (eg, by 5 to 10 mg/week over 4 to 6 weeks) per institutional standards – Patients can be switched to an equivalent/appropriate dose of oral corticosteroids (eg, prednisone) during the steroid taper

BAL = bronchoalveolar lavage; CMV = cytomegalovirus; COVID-19 = coronavirus 2019; CTCAE = Common Terminology Criteria for Adverse Events; DNA = deoxyribonucleic acid; HRCT = high-resolution computed tomography; ILD = interstitial lung disease; IV = intravenous; KL-6 = Krebs von den Lungen-6; PCR = polymerase chain reaction; PFT = pulmonary function test; PJP = Pneumocystis jiroveci fungus; RT-PCR = real-time polymerase chain reaction; SP-D = serum surfactant protein D; SpO2 = oxygen saturation.

Table 7 Dose Modification/Toxicity Management Recommendations for GI Toxicities

Adverse Reaction CTCAE v5.0 Grade/Severity	Recommended Management	Recommended Dosing Modification	Recommended Follow-up

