Grade 3 or 4 AST/ALT elevation (> 5 to 20 times ULN or from baseline, if baseline is abnormal)	
 • Evaluate differential diagnosis and causality (including pre-existing liver disease and infectious etiology) • Close monitoring for any clinical symptoms • Weekly monitoring of transaminase and bilirubin levels until return to Grade 1 or < 3 times ULN • Consider hepatic consult and treat accordingly per standard treatment guidelines • Permanently discontinue study drug if the patient meets the definition of Hy's law 
 ○ AST or ALT value > 3 × ULN and TBL > 2 × ULN ○ No other reason to explain combination of increased AST or ALT and TBL, ALP normal (ie, no initial findings of cholestasis) 	Withhold study drug	
 • If resolved to Grade 1 or baseline in less than 28 days, resume study drug at the same or a reduced dose at the discretion of the investigator • If not resolved to Grade 1 or baseline more than 28 days recommend restarting at a reduced dose • In case of Hy's Law or if suspicious of liver injury permanently discontinue study drug

ALP = alkaline phosphatase; ALT = alanine aminotransferase; AST = aspartate aminotransferase; COVID-19 = coronavirus 2019; CTCAE = Common Terminology Criteria for Adverse Events; RT-PCR = real-time polymerase chain reaction; TBL = total bilirubin level; ULN = upper limit of normal.

Table 9 Dose Modification/Toxicity Management Recommendations for Infection

Adverse Reaction CTCAE v5.0 Grade/Severity	Recommended Management	Recommended Dosing Modification	Recommended Follow-up
Grade 1 or 2 Infection	
 Evaluate differential diagnosis and causality (infection/immune-related/disease progression) with standard diagnostic tests (including but not limited to imaging, COVID-19 testing, chest X-ray, cultures, etc) Consider supportive care, including use of growth factors for patients with persistent or severe myelosuppression Once confirmed as infection, treat as per standard guidelines (including but not limited to antibiotics or antifungals) Consider infectious disease consult, as appropriate For patients with pulmonary or GI toxicities or myelosuppression, also refer to guidelines for management of those conditions 	Continue current dose	
 In case of persistent infection or worsening, manage as next higher grade

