BSA = body surface area; CTCAE = Common Terminology Criteria for Adverse Events; DRESS = drug reaction with eosinophilia and systemic symptoms; IV = intravenous; SJS = Steven's Johnsons' Syndrome; TENS = toxic epidermal necrolysis.

Table 14 Dose Modification/Toxicity Management Recommendations for Nausea/Vomiting

Adverse Reaction CTCAE v5.0 Grade/Severity	Recommended Management	Recommended Dosing Modification	Recommended Follow-up
Grade 1 or 2 Nausea or vomiting	
 • Initiate dietary modification (small frequent meals, bland foods, sipping/eating slowly) • Initiate antiemetic therapy as needed 	Continue current dose	
 • Reassess within 48 hours of starting supportive treatment • If responsive to antiemetic treatment: 
 ○ No change in study drug dose ○ Monitor as clinically indicated until complete resolution • If not responsive to antiemetic treatment or worsening 
 ○ Withhold study drug ○ In case of worsening, treat as Grade 3 or 4
Grade 3 Nausea or vomiting	
 • Initiate antiemetic therapy • IV hydration • Consider hospitalization • If persistent despite maximal supportive care and dose hold, investigate other causes (consider GI consult, imaging, CNS imaging) 	Withhold study drug	
 • If resolved in less than 28 days, resume study drug at the same or a reduced dose as per investigator’s discretion • If not resolved within 28 days, resume study drug at reduced dose • Consider using scheduled antiemetic prior to HMPL-523 administration for prophylaxis
Grade ≥ 4 Vomiting	
 • Initiate antiemetic therapy IV • IV hydration • Hospitalization for stabilization/management • If persistent despite maximal supportive care and dose hold, investigate other causes (consider GI consult, imaging, CNS imaging) 	Withhold study drug	
 • If resolved in less than 28 days, resume study drug at the same or a reduced dose as per investigator’s discretion • If not resolved within 28 days, resume study drug at reduced dose • Consider using scheduled antiemetic prior to HMPL-523 administration for prophylaxis

CTCAE = Common Terminology Criteria for Adverse Events; CNS = central nervous system; GI = gastroenterology; IV = intravenous.

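### Appendix 15 Tables 8 and 14 permit a restart at 28 days with no grade limit, Protocol 5.4.2 withholds until Grade ≤2, and no text says which governs

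*Protocol*

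**What the plan says.** **Protocol 5.4.2** covers Stage 1 after the DLT window and all of Stage 2. It opens permissively: at Grade 3 or 4 toxicity the dose "may be interrupted and/or reduced to the next lower dose level (600 mg) if any of the following are observed". Nausea and vomiting fall outside the nonhematologic trigger only if they are well controlled by medication. Once drug is held, the text is firmer:

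- "Treatment with HMPL-523 should be withheld until the toxicity resolves to CTCAE Grade" ≤2, after which dosing may resume at the same or the lower dose.
- "Consult with the sponsor if a treatment hold longer than 2 weeks is required for recovery from toxicity".
- If "dosing is interrupted for > 14 consecutive days due to toxicity, treatment should be discontinued, unless otherwise agreed between the investigator and the sponsor".

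**Protocol 5.4.3** sends sites to Appendix 15 for toxicity management, including dose modification. The Appendix 15 introduction describes its content as general recommendations to be supplemented by protocol-specific guidance. It advises talking to the sponsor if questions arise.

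**Appendix 15** withholds drug in each row at issue, then gives these restart lines:

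- Table 14, Grade 3 nausea or vomiting and, separately, Grade ≥4 vomiting: "If not resolved within 28 days, resume study drug at reduced dose".
- Table 8, Grade 3 or 4 AST/ALT: "If not resolved to Grade 1 or baseline more than 28 days recommend restarting at a reduced dose". The exception is Hy's Law, or "if suspicious of liver injury permanently discontinue study drug".
- Table 11, Grade 4 thrombocytopenia or any grade with bleeding: same-dose restart once the event is at a lower grade or baseline.

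**The concern.** The body text and the appendix give different restart conditions for the same event. A site that opens Table 8 or Table 14 at day 28 finds a restart line with no grade that must first be reached. Taken at its word, that line covers a patient whose vomiting or transaminases are still at Grade 3 or 4, where 5.4.2 says to keep withholding. What is at stake is re-exposure during an unresolved severe toxicity. No estimate or analysis is involved.

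**Working it through.** No figure in the plan needs reproducing. The check sets the texts side by side.

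**Step 1: a Grade 3 or 4 event, drug held, day 28.** The hold is 28 days against a 14-day limit in 5.4.2, so the sponsor-agreement rule already applies. Hy's Law and suspected liver injury are set aside, since Table 8 stops drug for both.

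| Residual grade at day 28 | 5.4.2 | Tables 8 and 14 | Compatible? |
|---|---|---|---|
| Grade 1 | Restart allowed with sponsor agreement | Table 14: reduced dose if Grade 1 counts as not resolved; Table 8: outside its unresolved line | Yes, if agreement is obtained |
| Grade 2 | Restart allowed with sponsor agreement | Reduced-dose restart (Table 8: if not at baseline) | Yes, if agreement is obtained |
| Grade 3 or 4 | Keep withholding, or discontinue | Reduced-dose restart | No |

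Only the last line conflicts, but nothing in either table excludes it.

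**Step 2: does the sponsor override cure the conflict?** In 5.4.2 the agreement clause is attached to the discontinuation rule after 14 days. It permits a patient to stay on study treatment despite a long hold. It is not attached to the Grade ≤2 restart condition.

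**Step 3: does the nausea and vomiting exception cure it?** It applies only to well-controlled events. A Grade 3 or 4 event still unresolved at 28 days would not normally qualify.

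**Step 4: what do other Appendix 15 rows do at 28 days?** Eight rows state an action for an unresolved event:

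- Three restart: Table 8 Grade 3/4, Table 14 Grade 3, Table 14 Grade ≥4.
- Four discontinue: Table 6 Grade 2 (only as something to consider), Table 6 Grade 3/4, Table 9 Grade ≥3 infection, Table 9 Grade ≥3 shingles. Table 6 Grade 3/4, for infectious or unclear cause, reads "If not resolved to baseline within 28 days, permanently discontinue study drug".
- One, Table 13 Grade 3 rash, discontinues under a different condition (unresolved after dose reduction), so it does not belong with the four.

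Thus 3 + 4 + 1 = 8. The appendix gives no reason for treating the three differently.

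**Step 5: Table 11.** A lower grade than Grade 4 includes Grade 3, which SAP Appendix 2 places at platelets from 25 to below 50 × 10⁹/L. The Grade 4 lines in Table 10 (ANC ≥1 × 10⁹/L) and Table 12 (Grade ≤2 or baseline) stay within 5.4.2; Table 11 does not. However, its first row continues the current dose at Grade ≤3 without bleeding, which the permissive opening of 5.4.2 allows. Restarting at non-bleeding Grade 3 agrees with that row.

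**Step 6: size of the reduced dose.** For a Stage 2 patient on 700 mg, the first reduction is to 600 mg: 600/700 = 0.857. A Table 8 or 14 restart after a first reduction is therefore at about 86% of full dose.

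**The case against.** The strongest reply is that no patient reaches day 28 without the sponsor being involved, because 5.4.2 requires consultation beyond 2 weeks and agreement beyond 14 days. Other text narrows the gap further. Protocol 5.7.3 requires discontinuation for intolerable toxicity, which 28 days of severe vomiting could well be. Protocol 2.3.2.1 withholds drug for any Grade ≥3 event indicative of hepatic injury. Table 8 has its own stop for suspected liver injury. Appendix 15 calls itself general recommendations and defers to clinical judgment. The Table 8 line is also awkwardly worded and can be read as addressing slow resolvers only.

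Most of this stands as mitigation. It makes an inappropriate restart unlikely, but it does not reconcile the texts: supplementing is not a precedence rule, and 5.4.3 names Appendix 15 as the place to look for these same toxicities.

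Three stronger inferences are tempting and should not be drawn.

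- A reader might infer that the protocol orders treatment through Grade 3 or 4 toxicity. It does not. The lines are silent on grade, fit 5.4.2 at Grade ≤2 with sponsor agreement, and Table 8 only recommends.
- A reader might infer that Table 11 is a safety error. Its agreement with its own first row, and a DLT definition (4.4) that counts Grade 3 thrombocytopenia only with bleeding or a transfusion need, suggest a deliberate choice that 5.4.2 fails to mention.
- A reader might count five discontinuing rows against three. Table 13's different condition makes it four, one of them only advisory.

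**Conclusion.** The inconsistency is real. Three lines (one in Table 8, two in Table 14) permit or recommend a restart without the Grade ≤2 condition of 5.4.2, and no text ranks the two. Table 11 is a cross-reference gap.

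The practical size is small. Enrollment is closed, about 3 patients were on treatment at Amendment 5, and sponsor contact is already required well before day 28. No endpoint, analysis set or planned analysis depends on it. The documents do not show that any patient has been restarted this way.

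The conclusion assumes that sites use the Appendix 15 tables as working instructions, as 5.4.3 invites them to. The point matters only while patients remain on drug. Amendment 5 moved the end of study from 1 to 2 years after the last patient's first visit, which lengthens that period. It is worth correcting because the correction costs so little.

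**What to change.** (a) Add one sentence to 5.4.3: the Grade ≤2 restart condition and the rule on holds over 14 days in 5.4.2 govern unless an Appendix 15 row is stricter or is a named exception.

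(b) Replace the unresolved-at-28-days lines in Table 8 (Grade 3/4) and in both Table 14 rows with: *restart at a reduced dose only if the event is Grade ≤2 (or baseline) and the sponsor agrees; otherwise continue to withhold or discontinue per 5.4.2*. Keep the 5.4.2 exception for well-controlled nausea and vomiting. This adds no compulsory discontinuation and leaves the investigator-sponsor agreement clause intact.

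(c) In Table 11, either state that Grade 4 or bleeding thrombocytopenia restarts at Grade ≤2 or baseline, or name non-bleeding Grade 3 thrombocytopenia as an exception in 5.4.2. Baseline must stay in the first option, because the note to exclusion criterion 2 (5.1.2) lets expansion patients enter with platelets below 50 × 10⁹/L with sponsor approval.

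The cost is a clarification letter or short amendment: one added sentence and four changed lines (one in Table 8, two in Table 14, and one in Table 11 or 5.4.2). There are no new procedures and no change to the SAP.

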5.4.3 Recommendations for Management of Toxicity Including Dose Modification

Recommendations for management of identified toxicities (pulmonary toxicities [including pneumonia/pneumonitis], gastrointestinal toxicities, hepatic toxicity, infection, neutropenia, thrombocytopenia, anemia, rash/cutaneous skin reactions, and nausea/vomiting), including dose modification, are provided in [Appendix 15](#). Approved prescribing information for other drugs used to treat relapsed or refractory lymphoma should be utilized to guide management of toxicities associated with these drugs.

5.5 Concomitant Therapy and Food

5.5.1 Permitted Therapy

Concomitant therapy includes any medication (eg, prescription drugs, over the counter drugs, homeopathic remedies, or nutritional supplements) used by a patient from 7 days prior to the screening visit to 30 days after the end of treatment or early termination. All such medications should be reported to the investigator and recorded on the Concomitant Medications page of the electronic case report form (eCRF).

